## 7.2. General Methodology

For FAS and PPS descriptive statistics will be used to summarize patient characteristics. This will include mean and standard deviation, minimum, maximum and median with the interquartile range [IQR] for continuous variables and counts and percentages for categorical variables. Summary statistics will be reported with maximum 2 decimals, as appropriate. Comparisons between phases have been performed using Wilcoxon's Test for continuous variables, while comparisons of categorical variables have been performed by means of the Chi-square test or Fisher exact test for extreme proportions, as appropriate. Statistical tests were based on a two-sided significance level of 0.05.

Analysis for specific objectives have been stated in the corresponding sections (7.9.1 and 7.9.2).

When comparison of clinical primary outcomes is conducted the propensity score method could be used to control for biases and confounding which may be due to the nature of this study.

It is anticipated that SAS (SAS Institute Inc., Cary, NC, USA) will be used to perform all statistical analyses. Statistical tests will be based on a two-sided significance level of 0.05.

## 7.3. Center Pooling

The study will involve more than one site and a center impact on primary outcome could be investigated. A description on primary outcome by site with 95% confidence intervals for each center will be provided, as appropriate. Additional exploratory analysis on baseline characteristics could be performed to check potential difference on primary outcome among sites.

## 7.4. Handling of Missing, Unused, and Spurious Data and Dropouts

Since the impact of missing data is expected to be small, no multiple imputation method for missing data is planned. However, the issue of missing data could arise; the choice of the imputation method for missing data will depend on the pattern of missing data and the type of the imputed variable.

The missing device data will not be imputed and the minimal device data requirement for inclusion is at least 90% of time continuously monitored.

Outliers and influential observations will be identified via graphical plots. Once identified outliers, or influential observations the study team will be informed and according to their decision the analysis for primary endpoint will be repeated excluding the outliers.

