## 12.3 Analysis of clinical data

Patient demographics and baseline characteristics will be presented using appropriate summary statistics. This includes mean and standard deviation, minimum, maximum and median with the interquartile range [IQR] for continuous variables and counts and percentages for categorical variables. Summary statistics will be reported with maximum 2 decimals, as appropriate. The SAS software (SAS Institute Inc., Cary, NC, USA) will be used to perform statistical analyses. Statistical tests will be based on a two-sided significance level of 0.05. Graphical representations will be used as deemed appropriate. No adjustments for multiple comparisons or multiple look at data will be performed. Outliers and influential observations will be identified via graphical plots and according to study team decision the analysis could be repeated excluding potential outliers. In case of missing data, no imputation method will be implemented for analysis.

The Full Analysis Set (FAS) will be used for primary final analysis. Any patient who does not satisfying the inclusion/exclusion criteria will be eliminate from the FAS population. Details of endpoints analyses and additional analysis will be described in the Statistical Analysis Plan. The analyses of primary objective on the proportion of patient with at least one RC markers will be reported together with their 95% confidence intervals and separately for each arm and phase of the study (see primary endpoint definition). When comparison of clinical primary outcomes is conducted the propensity score methods could be used to control for biases and confounding which may be due to the nature of this study. The

difference between the two groups within phase and between phases within groups will be analyzed by means of unpaired t-test or Mann-Whitney test according to the normal or non-normal distribution. For one secondary outcome the logistic regression model will be used to check potential predictors. Bivariate odds ratios (ORs) and 95% confidence intervals (95% CIs) will be estimated for each predictor. A multivariate logistic regression model will be performed according to univariate model's results. Other secondary outcomes will be performed using sensitivity and specificity analysis.

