## 6. Determination of Sample Size

The sample size calculation is based on primary endpoint and it was estimated using data from previous studies with a precision-based calculation. Recent data on post-surgical patient have shown a proportion of patient with the RC markers for the  $\text{SpO}_2 \leq 85\%$  for  $\geq 3$  minutes at 13% and for  $\text{RR} \leq 8$  or  $\geq 22$  bpm for  $\geq 3$  minutes at 1.4% in patients undergoing opioid therapy. Using this information, a minimum proportion of 10% of patients with RC markers with a sample size of 182 subjects will be able to obtain a 95% confidence level with a precision of 5% (ranging from 5% to 10%) and a power of at least 0.80 defined as the probability of achieving the desired precision. Considering a 10% withdrawal or potential dropouts and a potential attrition rate to monitoring compliance of 5% a total of approximately 210 subjects will be enrolled. This cohort will be used prospectively for the blinded and not blinded phase with a ratio 1:2 respectively to minimize not blinded monitored subjects. The blinded phase will enroll

70 subjects randomly allocated 1:1 in the Capnostream 20p and PM1000N arms while the not blinded phase will enroll 140 subjects with same randomized schedule.

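### The SAP expects missing data to matter little, yet plans to lose about 28 of 210 patients from the primary analysis, and no sensitivity analysis would show the effect

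*SAP*

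**What the plan says.** SAP section 7.4 rests its approach on an expectation: "Since the impact of missing data is expected to be small, no multiple imputation method for missing data is planned". It then leaves a way out, because if the issue arises "the choice of the imputation method for missing data will depend on the pattern of missing data" and on the type of variable. For device recordings, which Protocol section 8.10 makes the source for the number and duration of RC markers, the rule is firm: "The missing device data will not be imputed". Protocol section 12.3 is firmer still: "In case of missing data, no imputation method will be implemented for analysis".

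SAP section 6 sizes the study for "a minimum proportion of 10% of patients with RC markers". From 182 evaluable patients it aims at a half-width of 5 points at 95% confidence. It then inflates for loss: "Considering a 10% withdrawal or potential dropouts and a potential attrition rate to monitoring compliance of 5" per cent. The result is about 210 enrolled.

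The two documents name different primary sets. Protocol section 12.3 uses the FAS. SAP section 7.1.3 evaluates the primary endpoint and secondary endpoint 1 in the PPS only, which requires no major deviation and at least 24 hours of effective monitoring. Partial recordings from patients who fall short are used in the FAS only, and the SAP's table gives the FAS no role for the primary endpoint. Whether patients with under 90% continuous monitoring stay in the PPS is left open, and SAP section 7.12 allows both cut-offs to change.

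Both documents report the primary result separately by arm and phase (Protocol section 12.3, SAP section 7.9.1).

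**The concern.** The premise in SAP section 7.4 and the allowance in SAP section 6 do not fit together. At the design values the plan expects about 28 unevaluable patients and about 18 events among the evaluable ones. A method that sets aside more patients than it counts as events cannot be assumed to have little impact.

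The losses need not be random. Protocol section 8.12 lists adverse events and withdrawal for medical reasons among the possible reasons for leaving. A patient who deteriorates and leaves the ward before 24 hours may already have a recorded marker and would still drop out of the SAP's primary analysis. Protocol section 8.7 also ends monitoring at full mobilisation or discharge, so some short records may belong to patients doing well. The bias could run either way.

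The study's main task is to quantify an incidence. The planned interval carries sampling error only. The planned checks on the primary endpoint are a possible repeat without outliers (SAP section 7.4) and a description by site (SAP section 7.3), and neither addresses missing patients.

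**Working it through.** **Inputs.** Design incidence 10%, 182 evaluable, 95% confidence, 5-point half-width, assurance 0.80, loss 10% plus 5%, 210 enrolled (all SAP section 6). Phase I has 35 patients per arm and Phase II has 70. Assumption: losses spread evenly, giving 30 of 35 and 60 of 70 evaluable.

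**The plan's own figure.**
- The smallest n for which the exact (Clopper-Pearson) 95% interval has half-width at most 5 points with probability at least 0.80, at 10% incidence, is 179. At 182 that probability is 0.855. The SAP's 182 is reproduced to within 3%.
- Inflation: 182 × 1.15 = 209.3; 182 × 1.10 × 1.05 = 210.2; 182 / (0.90 × 0.95) = 212.9; 182 / 0.85 = 214.1. All are close to 210.
- Protocol section 12.1 gives 260 evaluable, from which the same steps give 299 to 306. The 210 follows from the SAP's 182, not from 260.

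**Expected loss.** 210 − 182 = 28, and 28/210 = 13.3%. The nominal allowance is 10% + 5% = 15%.

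**Extreme bounds.** With x events among n evaluable, m of unknown status and N = n + m, the lower bound is x/N, the upper bound is (x + m)/N and the width is m/N. The confidence interval is the exact interval for x/n.

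| Estimate at about 10% | x/n | 95% CI | CI width | Bound | Bound width |
|---|---|---|---|---|---|
| Pooled, N = 210 | 18/182 | 6.0% to 15.2% | 9.2 | 8.6% to 21.9% | 13.3 |
| Phase I arm, N = 35 | 3/30 | 2.1% to 26.5% | 24.4 | 8.6% to 22.9% | 14.3 |
| Phase II arm, N = 70 | 6/60 | 3.8% to 20.5% | 16.7 | 8.6% to 22.9% | 14.3 |

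By arm, the bound is 14.29/24.42 = 59% of the interval width in Phase I and 14.29/16.75 = 85% in Phase II. It adds to sampling error and does not replace it. If all five unknown patients in a Phase I arm had a marker, 3/30 would become 8/35 = 22.9%, with an exact interval of 10.4% to 40.1%.

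**Dependence on incidence.** The bound is wider than a Wald interval of width 2 × 1.96 × √(p(1 − p)/n) only when p is below about 30% pooled, 9% in a Phase II arm and 4% in a Phase I arm (mirrored at very high p). At 67/182 = 36.8% pooled, the exact width is 14.5 points and the bound 67/210 to 95/210 is 13.3 points wide.

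**Intermediate scenarios, pooled.**
- Risk in the 28 at 2, 3 and 5 times 10%: (18.2 + 28 × 0.20)/210 = 11.3%; (18.2 + 28 × 0.30)/210 = 12.7%; (18.2 + 28 × 0.50)/210 = 15.3%.
- Odds at 1.5, 2 and 3 times the observed 18/164 give risks of 14.1%, 18.0% and 24.8% in the 28. The overall figures are (18 + 28 × 0.141)/210 = 10.5%, (18 + 28 × 0.180)/210 = 11.0% and (18 + 28 × 0.248)/210 = 11.9%.

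**The case against.** The strongest reply is that a reader might infer that uncertainty from missing patients exceeds the confidence interval wherever the incidence is reported. The documents do not support that. They report by arm and phase, where at 10% the interval is the wider of the two. Even pooled, the inference depends on an incidence that SAP section 6 calls a minimum. Protocol section 3.1 cites up to 37% of non-cardiac surgical patients with saturation below 90% for over an hour, and near that value the pooled comparison reverses. At 67 events it is also no longer true that unevaluable patients outnumber events. This part of the reply stands.

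A reader might also infer that the planned interval has been shown to be wrong. It has not. Two to three times the risk in the missing patients leaves the pooled figure inside 6.0% to 15.2%. It takes about five times the risk to reach the upper limit, and no document figure supports that.

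Three further points have weight.
- The 10% and 5% are planning allowances, and actual exclusions may be smaller or larger.
- The sentence about small impact may be meant for variables other than device data, which have their own rule. On that reading, though, no assessment of the effect of missing device data exists at all.
- Many excluded patients will have partial recordings, and one recorded marker settles their status. The bounds above are therefore the widest case. This points to using those recordings, which the SAP's primary analysis does not do.

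The study is also a descriptive pilot, which limits the consequences. But estimating incidence is its primary objective, so the pilot label does not remove the need for the check.

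**Conclusion.** The concern holds, within limits. The SAP's premise is not reconciled with its own planned loss of 13% to 15%. The SAP's primary set discards patients whose outcome may already be known, the Protocol names a different set, and no analysis shows what the losses do to the estimate.

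At the 10% design value the undisclosed range is at most 13.3 points pooled and 14.3 points by arm and phase. Only the pooled bound is wider than its confidence interval. These figures assume 28 lost of 210, even spread over arms and phases, and nothing known about any lost patient. The direction of any bias cannot be told from the documents. The point is worth correcting before analysis, but it does not invalidate the design.

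**What to change.** 1. In SAP section 7.4, delete the statement that the impact is expected to be small.
2. Reconcile the primary analysis set between Protocol section 12.3 (FAS) and SAP section 7.1.3 (PPS), and the evaluable number between Protocol section 12.1 (260) and SAP section 6 (182).
3. For each arm and phase, report the primary proportion in the FAS from all available recordings, counting any patient with a recorded marker as an event however short the recording.
4. Beside it, give best-case and worst-case bounds for enrolled patients whose status is still unknown, including any who were never monitored and so fall outside the FAS.
5. Add intermediate scenarios on the odds scale, for example odds of 1.5, 2 and 3 times the observed. Multiples of the risk itself fail at higher incidence: three times is impossible above 33%.

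The cost is a few lines of text and one extra table from data already collected. The reported range will be wider and less favourable.

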## 7.5. Adjustments for Multiple Comparisons

No adjustments for multiple comparisons or multiple look at data will be performed.

## 7.6. Demographic and Other Baseline Characteristics

Descriptive statistics will be used to summarize demographic and baseline characteristics, medical history and vital signs variables for both FAS and PPS. This will include mean, standard deviation, median, minimum, and maximum for continuous variables, and counts and percentages for categorical variables.

To compare characteristics between phases the Chi-Square' Test will be used for categorical variables and the Wilcoxon's Test will be used for continuous variables.

Demographic and Baseline variables will be collected through OC and described with Tables, Listings and Figures as appropriate.

**Table 5 - Subject Demographics and baseline characteristics– FAS****Table 6 - Subject Demographics and baseline characteristics – PPS****Table 7 - Subject Medical History – FAS****Table 8 - Subject Medical History – PPS****Table 9 - Subject Vital Signs – FAS****Table 10 - Subject Vital Signs – PPS**

## **7.7. Treatment Characteristics**

Extent of exposure in the population is characterized according to the duration of the study with routine monitoring.

Duration of Monitoring Exposure will be measured in minutes from the start of the monitoring through and including the time of monitoring end: Duration of monitoring exposure (minutes) = (End monitoring date/time – Start monitoring date/time). Extent of exposure will be presented in a summary table and supporting data listing.

Duration of Study Exposure will be measured in days starting from the point of enrollment (informed consent completed and inclusion/exclusion criteria confirmed per the screening evaluation) through and including the time of study exit: Duration of study exposure (days) = (Study Exit date – date of enrollment). Extent of study exposure will be presented in a summary table and supporting data listing.

Descriptive statistics will be used to summarize treatment characteristic variables for both PPS and for FAS. This will include mean, standard deviation, median, minimum, and maximum for continuous variables, and counts and percentages for categorical variables.

**Table 11 – Monitoring Exposure – FAS****Table 12 - Monitoring Exposure – PPS****Table 13 – Study Exposure – FAS****Table 14 - Study Exposure – PPS**

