## 8.4 Patient Consent

The investigator or authorized designee must obtain written informed consent before any clinical study related activity takes place. Written informed consent must be obtained prior to surgery.

In advance of the consent discussion, the patient should receive the EC approved Patient Information and Informed Consent Form. During the consent discussion, the investigator or his/her authorized designee must fully inform the patient of all aspects of the clinical study that are relevant to the patient's decision to participate in the clinical study. If a patient is illiterate, an impartial witness must be present during the entire informed consent discussion. All items addressed in the Patient Information and the Informed Consent Form must be explained. The language used shall be as non-technical as possible and must be understandable to the patient and the impartial witness, where applicable.

The patient must have ample time and opportunity to read and understand the Patient Information and the Informed Consent Form, to inquire about details of the clinical study, and to decide whether or not to participate in the clinical study. All questions about the clinical study should be answered to the satisfaction of the patient.

Neither the investigator, nor the investigation site staff shall coerce or unduly influence a patient to participate or to continue to participate in the clinical study. The informed consent process shall not waive or appear to waive the patient's rights.

When the patient decides to participate in the clinical study, the Informed Consent Form must be signed and personally dated by the patient and investigator or authorized designee. If applicable, the witness shall also sign and personally date the consent form to attest that the information in the Patient Information and Informed Consent Form was accurately explained and clearly understood by the

patient, and that informed consent was freely given. Detailed documentation of the process must be recorded in the patient's case history.

After all persons have signed and dated the Informed Consent Form, the investigator must provide the patient with a copy of the Patient Information and the Informed Consent Form.

Medtronic will inform the investigators whenever information becomes available that may be relevant to the subject's confirmed participation in the clinical study. The investigator or his/her authorized designee should inform the patient in a timely manner.

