**Table 3 - Protocol Deviation by Reason - FAS**

**Table 4 - Protocol Deviation by Visit - FAS**

**Listing 1 - Other deviations – FAS**

### 7.1.3. Analysis Sets

The following patient sets will be used for the analysis:

- The Full Analysis Set (FAS) includes all patients actively enrolled in the study, who signed Informed Consent Form (ICF), fulfilled the inclusion/exclusion criteria and monitored by CS20p or PM1000N. The FAS will be used to describe both baseline characteristics and safety outcomes of the study population;
- The Per Protocol Set (PPS) includes all patients in the FAS, without major protocol deviations, who have at least 24 hours of monitoring *effective time*. The PPS will be used to describe baseline characteristics of the study population and to evaluate the primary and secondary endpoints. Patient with poor quality of device data, defined as having less than 90% of time continuously monitored, will be included or excluded from the PPS, as appropriate.

The following table shows how each population set will be used for analyses:

Population set	Baseline assessment	Primary and Secondary Endpoint #1	Secondary Endpoints #2, #3, #4 and #5	Safety AE Death
FAS	✓		✓	✓
PPS	✓	✓	✓	

For those patients who have less than 24 hours or poor quality of device data monitoring or who withdrew, the analyses will include all data up to the point of their last data collection only for FAS population.

An additional set could be created during the analysis phase, in case necessary to investigate on a particular subgroup of patients.

 Effective time is the cumulative time with valid recorded data. This aimed to filter out periods of time where the patient was not connected to the Capnography cannula or pulse-ox sensor, but recording was on-going (the patient was not monitored during this time).

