### 7.9.2. Secondary Endpoints

The secondary endpoints are:

1. To compare phases in terms of Primary endpoint incidence;
2. To compare phases in terms of respiratory and SAE incidence, number of ICU transfers and related length of stay, Code blues and RRT responses.
3. To evaluate the rate of clinical early interventions performed by nurse staff to prevent a potential AE, introducing continuous monitoring devices connected to a remote monitoring platform;
4. To evaluate the nurses’ satisfaction related to the monitoring system introducing continuous monitoring devices connected to a remote monitoring platform;
5. To establish the Predictive values of  $\text{EtCO}_2$ , RR,  $\text{SpO}_2$ , plethysmography-derived RR, IPI and EWS in respect to respiratory and other SAE.

In order to evaluate secondary **endpoints #1 and #2**, the incidence of events will be reported together with the comparison between phases, by means of the Chi-square test or Fisher exact test for extreme

proportions, as appropriate. If the monitoring/study exposure results different between phases, also the rates of events will be reported, together with the 95% Poisson Confidence Intervals. The Poisson regression model will be used to calculate the Incidence Rate ratio (IRR), with the d-scale option.

For **endpoint #3**, the rate of clinical early interventions will be calculated as (number of early interventions)/(total time-person in FAS) and it will be reported together with the 95% Poisson Confidence Interval.

Early interventions include, as defined in CRF (Monitoring Period):

1. Stimulated subject to breathe;
2. Repositioned/opened airway;
3. Held or reduced Respiratory Depressive (RD);
4. Added or increased supplemental oxygen;
5. Ventilation support;
6. Other

**Endpoint #4** will be evaluated reporting a summary of the nurses' satisfaction answers.

To identify the predictive values for EtCO2, RR, SpO2, plethysmography-derived RR, IPI and EWS, which can predict respiratory and other SAE, a sensitivity analysis will be performed (**endpoint #5**), and the following parameters will be reported, for each RC marker:

1. **Sensitivity** = 
$$\frac{(\# \text{ of clinical events "Yes" and with RC marker "Yes"})}{(\# \text{ of clinical events "Yes"})} = \frac{TP}{(TP+FN)}$$
2. **PPV** = 
$$\frac{(\# \text{ of clinical events "Yes" and with RC marker "Yes"})}{(\# \text{ of events with RC marker "Yes"})} = \frac{TP}{(TP+FP)}$$

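### RC-marker rates in the SAP have no named clock; on its only monitoring-time formula they include disconnected and post-event time and come out too low

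*SAP*

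**What the plan says.** **RC-marker rates.** SAP 7.9.1 divides the number of patients with at least one RC marker by total person-time in the PPS, by arm and phase, with 95% confidence intervals. It does not say how person-time is measured. A physician at the other site adjudicates each patient's candidate episodes, starting with the most likely one, and stops once one is accepted.

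**Exposure.** SAP 7.7 defines two durations. For the first, "Duration of Monitoring Exposure will be measured in minutes from the start of the monitoring through and including the time of monitoring end"; the formula is end minus start, with nothing deducted. For the second, "Duration of Study Exposure will be measured in days starting from the point of enrollment", and it runs to study exit. Both are presented as descriptive tables. Neither is named as a rate denominator.

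**Phase comparison.** For endpoints #1 and #2, SAP 7.9.2 says: "If the monitoring/study exposure results different between phases, also the rates of events will be reported". A Poisson incidence rate ratio (IRR) follows. Early interventions (endpoint #3) are divided by person-time in the FAS, again with no clock named.

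**Valid time.** The footnote to SAP 7.1.3 states: "Effective time is the cumulative time with valid recorded data". It removes periods off the cannula or the oximeter sensor, but is used only for the 24-hour PPS entry rule. SAP 7.4 requires at least 90% of time continuously monitored. SAP 7.1.3 lets patients below that be kept or dropped case by case, and 7.12 allows the cut-off to change.

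**Enrolment.** Protocol 8.4 states: "Written informed consent must be obtained prior to surgery". Enrolment also needs confirmed eligibility (Protocol 8.5). The FAS is limited to patients who "fulfilled the inclusion/exclusion criteria and monitored by CS20p or PM1000N".

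**The concern.** An RC marker cannot be detected while the relevant sensor is off. A patient whose RC has been accepted cannot supply another event, because adjudication has stopped. Both kinds of time enlarge the denominator and can add nothing to the numerator, so the rate falls below the rate during time at risk.

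The rate is one of the two forms in which the primary endpoint is reported (SAP 7.9.1 asks for a proportion and a rate), and Protocol 9.2 says the data may help to design a later outcome study.

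There is also a reason to expect the connected share to differ by phase. In Phase I alarms are silent and screens blinded, and fit depends on a regular check. In Phase II alarms sound, those from a displaced sensor or line are classed as false positives (Protocol 8.7), and the example algorithm in Appendix B tells staff to correct placement.

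**Working it through.** The documents give no event rate, person-time or rate ratio, so there is no figure on this point to reproduce. The SAP's sample size is not in dispute. At a proportion of 10%, an exact (Clopper-Pearson) 95% interval has half-width of at most 5% with probability 0.855 at n = 182, and 182 × 1.15 = 209.3, about 210. The 10% used below is that planning proportion. Higher incidences are assumptions.

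**Step 1, disconnection.** Let c be the connected share of clock time, with the 90% rule read as c ≥ 0.90. Reported rate / true rate = c.
- 90% rule enforced: 0.90 to 1.00, an understatement of at most 10%.
- Rule waived or changed: no bound in the documents.

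**Step 2, disconnection and the phase IRR.** With equal true rates, IRR = c(Phase II) / c(Phase I).
- Equal shares: 1.00.
- Extremes under the 90% rule: 0.90/1.00 = 0.90 and 1.00/0.90 = 1.11.
- Rule waived, assumed shares of 70% in Phase I and 90% in Phase II: 0.90/0.70 = 1.29 (0.78 if reversed).

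**Step 3, time after the event.** Assume a constant hazard and equal monitoring length, and let P be the proportion with an event. Events over all time, divided by the true rate, is P / (−ln(1 − P)).
- P = 10%: 0.10/0.1054 = 0.95.
- P = 30%: 0.30/0.3567 = 0.84.
- P = 50%: 0.50/0.6931 = 0.72.

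This factor cancels in the phase IRR when incidence is the same in both phases, and not otherwise. Steps 1 and 3 multiply: at c = 0.90 the reported rate is 0.90 × 0.949 = 0.85 of true at 10% incidence and 0.90 × 0.721 = 0.65 at 50%.

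**Step 4, against sampling error.** With 70 and 140 patients and 10% incidence there are 7 and 14 events. The standard error of log IRR is √(1/7 + 1/14) = 0.463, so the 95% limits around an IRR of 1 are 0.40 to 2.48. A shift to 0.90 raises a nominal 5% error rate to 5.6% at 10% incidence and 8.0% at 50% (normal approximation, no overdispersion).

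**Step 5, study exposure for endpoint #2 (secondary).** Assume 1 to 3 days from enrolment to surgery, 5 to 14 days from surgery to exit, and no countable event before surgery. The post-operative rate is understated by 1 − 14/15 = 7% to 1 − 5/8 = 38%. The null IRR is 1.00 if lead times are equal. If they average 1 day in Phase I and 3 in Phase II, it is 6/8 = 0.75 (5-day stay) to 15/17 = 0.88 (14-day stay). The documents give neither lead times nor stays. They also disagree on when exposure ends: Protocol 8.8 puts exit at discharge, while Protocol 5.1 and SAP 5.1 give 72 hours as the maximum time in study.

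**The case against.** The strongest reply is that SAP 7.7 is descriptive and never says its durations are the denominators. An analyst could use effective time without departing from the text. That stands: understatement follows from one reading, though 7.9.2 uses the 7.7 terms to trigger the phase rates and 7.9.1 itself counts all PPS person-time.

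It can also be said that the provision in 7.9.1 for a GEE adjustment when episodes per patient are unbalanced implies that repeat episodes count, so post-event time belongs in. That does not fit a rule that stops at one accepted RC.

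A reader might infer more than the documents support:
- **Pre-operative days dilute the RC-marker rates.** They cannot if monitoring time is used, because monitoring starts on ward arrival (Protocol 8.7).
- **Adverse-event rates have mismatched windows.** Events are collected from enrolment to exit (Protocol 8.1), so the windows largely match. Enrolment needs confirmed eligibility, so it may also be later than consent. What remains is that a patient who dies or is diverted before ward monitoring never enters the FAS, and that events before monitoring cannot reflect its effect.
- **Device rate ratios are biased.** The SAP plans no comparison between arms (7.1.1), and the arms use four and two markers. Rates are, however, printed by arm, and Protocol 12.3 still mentions differences between groups within phase.
- **The primary proportion or its tests are affected.** They use no person-time.

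**Conclusion.** The concern holds in a limited form. The denominator of the RC-marker rates is undefined. If the SAP's only monitoring-time formula is used and all PPS time is counted, those rates are too low: by up to 10% from disconnection with the 90% rule enforced and by an unknown amount without it, and to about 0.95 (10% incidence) or 0.72 (50%) of the true rate from post-event time under a constant hazard. Post-event time may therefore matter more than disconnection.

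With no true effect, disconnection moves the phase IRR within 0.90 to 1.11 under the 90% rule, and only if the connected share differs between phases. At 10% incidence that shift is small beside sampling error. Proportions and chi-square or Fisher tests are unaffected. The documents do not support a claim that every rate is biased, or that a planned device comparison is. The endpoint #2 point is secondary, and its size depends on lead times that the documents do not give.

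**What to change.** In SAP 7.7, 7.9.1 and 7.9.2, name the clock for each rate.

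- **RC-marker rates:** use valid recorded time, ending at the onset of the adjudicated RC episode. Use effective time for the composite and channel-specific valid time for each separate marker, because oximetry may be valid while the cannula is off. State whether an episode on one channel counts in the composite when the other channel is disconnected.
- **Adjudicated onset:** state that this may not be the earliest episode, because review starts with the most likely one. If an earlier true RC exists, some post-event time remains in the denominator. The Detection Tool groups episodes up to 30 minutes apart (SAP 10.1), so the adjudication record must identify the episode accepted.
- **Early interventions:** use clock time from monitoring start, since staff actions are observed whether or not a sensor is attached.
- **Endpoint #2 rates:** start exposure at ward monitoring start, list earlier adverse events separately, and settle when study exit occurs.

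The cost is SAP wording and two extra derived variables, from device memory and dates already collected, plus the onset time in the adjudication record. The downside is that the endpoint #2 rate would no longer cover the whole adverse-event window from enrolment to exit.
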